6.1 Between-group comparisons at each follow-up

At 4, 8 and 12 months, the proportions of patients with and without sensory deficit (0 vs. 1) will be summarized for each group.

- For **between-group comparisons** (Vivostat vs. Standard) at each time point, a **Chi-squared test** will be performed when expected cell counts are adequate. If assumptions are not met, **Fisher's exact test** may be used.
- In the current dataset, statistical significance is expected at 8 months ($p < 0.05$) and 12 months ($p < 0.01$), but not at 4 months.

Results will be reported as in Table 3, with counts, percentages, and p-values.

6.2 Within-group change over time

To assess changes in sensory deficit over time (4 vs. 8 vs. 12 months):

- For **overall comparison across the three time points** within each group and in the total sample, **Cochran's Q test** will be used.
- If Cochran's Q test is significant, **pairwise McNemar's χ^2 tests** will be used to compare:
 - 4 vs. 8 months,
 - 4 vs. 12 months,
 - 8 vs. 12 months.

Bonferroni correction will be applied for these three pairwise tests ($\alpha = 0.05/3 \approx 0.0167$). The corrected p-values and interpretation will be presented as in Table 4.

These analyses identify the postoperative interval with the most pronounced sensory recovery (in the current study: mainly between 4 and 8 months in the Vivostat group, with stabilization thereafter).

7. Power Calculation

Study Protocol Title: Impact of Platelet-Rich Fibrin on Donor Site Regeneration and Functional Recovery after ACL Reconstruction with BPTB Autograft

Version 01, 21 September 2020

After completing data collection, a **post-hoc power calculation** for the primary endpoint at 12 months will be performed:

- Observed proportions without sensory deficit at 12 months:
 - Vivostat group: 79% (0.79),
 - Standard group: 34% (0.34).
- Group sizes: $n_1 = 24$ (Vivostat), $n_2 = 29$ (Standard).
- Test: two-sided pooled z-test for difference in proportions, $\alpha = 0.05$.

The achieved power for detecting this difference is **0.93**, indicating that, despite being a pilot study, the sample size was sufficient to detect the observed effect size at 12 months with high probability.

This power calculation is descriptive and does not change the interpretation of the primary analysis.

8. Handling of Missing Data

In the conducted study all 53 patients completed follow-up; therefore, **no imputation of missing data** was necessary.

For the purposes of the statistical plan:

- In the event of missing follow-up data for future or extended analyses, only **complete-case analyses** will be performed (patients with available data for a given endpoint).
- The number and proportion of patients with missing data for each time point and endpoint would be reported descriptively.
- No multiple imputation or advanced methods are planned, given the pilot nature and small sample size.

9. Sensitivity and Exploratory Analyses

Given the modest sample size, no predefined subgroup analyses are planned. However, exploratory analyses could include:

- graphical presentation of sensory recovery over time in both groups (e.g., line plot of proportions without deficit, as in Figure 6),
- exploratory correlations between sensory deficit and subjective scores at 12 months (using Spearman correlation).

Study Protocol Title: Impact of Platelet-Rich Fibrin on Donor Site Regeneration and Functional Recovery after ACL Reconstruction with BPTB Autograft

Version 01, 21 September 2020

All such analyses will be clearly labeled as exploratory.

10. Deviations from the SAP

Any deviations from the planned statistical methods (e.g., use of alternative tests due to distributional assumptions) will be documented, justified and reported in the final manuscript or registry entry.

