Study Protocol Title: Impact of Platelet-Rich Fibrin on Donor Site Regeneration and Functional Recovery after ACL Reconstruction with BPTB Autograft

Version 01, 21 September 2020

COVER PAGE

Study Protocol Title : Impact of Platelet-Rich Fibrin on Donor Site Regeneration and Functional Recovery after ACL Reconstruction with BPTB Autograft

Version/Date: Version 01, 21 September 2020

NCT number: Not Available

Statistical Analysis Plan (SAP)

Study title: Sensory deficit following anterior cruciate ligament reconstruction with bone patellar-tendon bone autograft: platelet-rich fibrin (PRF) could provide a solution

Design: Single-center prospective cohort pilot study with two parallel groups (PRF / Vivostat group vs. Standard group) and repeated follow-up measurements

Sample size: 53 male patients (Vivostat n = 24; Standard n = 29)

Primary endpoint: Sensory deficit at the donor site over time (4, 8 and 12 months)

Secondary endpoints: Subjective knee function scores (Modified Cincinnati, IKDC, Tegner Lysholm, Tegner Activity Score); demographic and perioperative characteristics; safety

1. Analysis Populations

- **Full Analysis Set (FAS):** All patients who met inclusion criteria, underwent ACL reconstruction with BPTB autograft, were assigned to one of the two cohorts (Vivostat vs. Standard) and had at least one postoperative follow-up assessment. All efficacy analyses (sensory deficit and subjective scores) will be based on the FAS.
- **Safety Set:** All operated patients for whom group assignment (Vivostat vs. Standard) is known. Safety (complications, adverse events) will be summarized descriptively in this set.

No separate per-protocol analysis is planned because all 53 included patients completed follow-up according to the study results.

2. Endpoints

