2.2 Secondary endpoints

Secondary endpoints include:

- **Subjective functional scores:**
 - Modified Cincinnati score (continuous),
 - IKDC score (continuous),
 - Tegner Lysholm score (continuous),
 - Tegner Activity Score (ordinal/continuous).Each is measured preoperatively (baseline) and at 12 months postoperatively.
- **Demographic and perioperative characteristics:**
 - Age (years),
 - Body mass index (BMI, kg/m²),
 - Time from injury to surgery (months),
 - Length of hospitalization (days).

These are used to describe and compare the two groups at baseline.

- **Safety endpoints:** Clinical complications (infection, wound problems, thromboembolic events, range of motion restriction, graft rupture) observed during follow-up. These are summarized descriptively (frequency and percentage in each group).

3. General Statistical Principles

- All statistical tests will be **two-sided**.
- The nominal significance level is **p < 0.05**.
- For multiple pairwise comparisons of the same endpoint (e.g., sensory deficit across the three follow-up time points), **Bonferroni correction** will be applied ($\alpha_{\text{corrected}} = 0.05 / \text{number of comparisons}$).

Study Protocol Title: Impact of Platelet-Rich Fibrin on Donor Site Regeneration and Functional Recovery after ACL Reconstruction with BPTB Autograft

Version 01, 21 September 2020

- Continuous variables will be summarized as **mean, standard deviation, median and range**.
- Categorical variables will be summarized as **absolute frequencies and percentages**.
- The distribution of continuous variables will be assessed using the **Kolmogorov–Smirnov** and **Shapiro–Wilk** tests. Because most continuous variables deviate from normality or sample sizes are modest, **non-parametric tests** will be used for between- and within-group comparisons.

All analyses will be performed using **R software**, version 4.3.1 (2023-06-16).

4. Baseline Comparisons

Baseline comparability of the Vivostat and Standard groups will be assessed for:

- age, BMI, time from injury to surgery, length of hospitalization.

Since these are continuous variables, they will be compared between groups using the:

- **Wilcoxon rank-sum test** (Mann–Whitney U test).

Results will be presented as in Table 1 (mean, SD, median, range, and p-values). These analyses are descriptive and serve to document the similarity of groups at baseline in this non-randomized cohort.

5. Analysis of Subjective Functional Scores

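### SAP 6.2 names a recovery interval for the Vivostat group from within-group tests that compare neither the change between groups nor the two intervals with each other

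*SAP*

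**What the plan says.** SAP 2.1 lists two focuses for the primary endpoint: the between-group comparison of deficit proportions at each visit, with emphasis on 12 months, and the within-group change across 4, 8 and 12 months.

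SAP 6.1 covers the first with a chi-squared (or Fisher) test at each visit. SAP 6.2 covers the second. Cochran's Q is run "within each group and in the total sample"; if it is significant, three pairwise McNemar chi-squared tests follow at 0.05/3. The section then states: "These analyses identify the postoperative interval with the most pronounced sensory recovery". In parentheses it gives the result: "mainly between 4 and 8 months in the Vivostat group, with stabilization thereafter".

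Neither document plans a group-by-time term, a longitudinal model, a between-group comparison of change, or a comparison of the 4-8 month gain with the 8-12 month gain.

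**The concern.** Protocol section 2 sets the primary objective as the effect of PRF. A sentence that singles out one arm and dates its recovery invites the reading that PRF determines when sensation returns. That reading needs the between-group difference in change. A significant result in one arm beside a non-significant result in the other is not a test of that difference, and sensation may return without PRF. SAP 4 describes the cohort as non-randomized, so change within one arm cannot be credited to the treatment.

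The sentence has a second gap, even as a description of Vivostat alone. Calling one interval the larger, and saying recovery then levels off, compares two gains. Under 6.2 this rests on one p-value passing 0.0167 and another not passing it.

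At stake is a secondary timing statement that could be carried into the report as a PRF finding.

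**Working it through.** **Inputs.** Group sizes are 24 Vivostat and 29 Standard (SAP header). Tests are two-sided at 0.05 (SAP 3), with pairwise level 0.05/3 = 0.0167 (SAP 6.2). Proportions without deficit at 12 months are 0.79 and 0.34 (SAP 7), which fit 19/24 and 10/29. Follow-up is complete (SAP 8). No 4- or 8-month counts are given, so everything about change below is assumed.

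**The plan's own figure.** SAP 7 gives power 0.93 for the 12-month difference.
- Pooled proportion: (24×0.79 + 29×0.34)/53 = 0.544.
- Standard error under the null: √[0.544×0.456×(1/24 + 1/29)] = 0.1374.
- Standard error under the alternative: √[0.79×0.21/24 + 0.34×0.66/29] = 0.1210.
- Power: Φ[(0.45 − 1.96×0.1374)/0.1210] = Φ(1.49) = 0.93.

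This reproduces, but it concerns status at 12 months, not change.

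**Step 1: separate tests when both groups recover alike.** Assume each patient recovers between 4 and 8 months with probability q in both groups, nobody relapses, and the Cochran gate is ignored. With one-way changes, McNemar passes 0.0167 at 6 or more changes (chi-squared, uncorrected, p = 0.0143), 7 or more (exact, p = 0.0156) or 8 or more (chi-squared, continuity-corrected, p = 0.0133). Let A and B be the binomial probabilities of reaching the threshold with n = 24 and n = 29. Then P(opposite verdicts) = A(1−B) + B(1−A), and P(Vivostat only) = A(1−B).

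Example, exact test, q = 0.25: A = 0.393 and B = 0.613, so Vivostat only = 0.152, Standard only = 0.372 and opposite verdicts = 0.524.

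| q | Uncorrected: opposite / Vivostat only | Exact: opposite / Vivostat only | Continuity-corrected: opposite / Vivostat only |
|---|---|---|---|
| 0.15 | 33% / 10% | 18% / 5% | 8% / 2% |
| 0.20 | 51% / 16% | 41% / 12% | 26% / 7% |
| 0.25 | 46% / 13% | 52% / 15% | 47% / 13% |
| 0.30 | 28% / 7% | 43% / 11% | 52% / 14% |
| 0.40 | 5% / 1% | 11% / 2% | 23% / 5% |
| 0.50 | 0.4% / 0.03% | 1.2% / 0.1% | 3.6% / 0.4% |

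Most opposite verdicts are Standard only, because that group is larger.

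**Step 2: two intervals within Vivostat.** Assume equal true gains in 4-8 and 8-12 months, 15-30% of patients each, no relapse. Exactly one interval then passes 0.0167 in about 4-63% of studies, depending on the gain and the McNemar version. Half of these point to 4-8 months.

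**Step 3: a hypothetical data set that fits the stated results.** Suppose patients without deficit at 4, 8 and 12 months number 7, 15 and 19 of 24 in Vivostat, and 4, 9 and 10 of 29 in Standard, with no relapse.
- Between groups, uncorrected chi-squared gives p = 0.17, 0.022 and 0.001. This matches the pattern in SAP 6.1: significant at 8 and 12 months, not at 4.
- Cochran's Q is 18.7 (p < 0.001) in Vivostat and 10.3 (p = 0.006) in Standard, so both groups pass the gate.
- McNemar 4 v 8: 8 changes in Vivostat, p = 0.005; 5 in Standard, p = 0.025 (0.013 and 0.074 with continuity correction). Only Vivostat passes 0.0167.
- McNemar 8 v 12 in Vivostat: 4 changes, p = 0.046 (0.134 corrected). It does not pass.

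Under 6.2 this would be read as recovery in Vivostat mainly from 4 to 8 months and then a plateau. The direct contrasts do not establish it:
- Between groups, 4-8 months: 8/24 − 5/29 = 33.3% − 17.2% = 16.1 points, Newcombe 95% CI about −7 to 38, Fisher p = 0.21.
- Within Vivostat, 8 changes against 4: (8 − 4)/24 = 16.7 points. The standard error is √(12 − 4²/24)/24 = 0.140, giving a 95% CI of about −11 to 44. The exact binomial p for 8 of 12 is 0.39.

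**The case against.** The strongest reply is that 6.2 is headed and specified as a within-group analysis, and SAP 2.1 lists that aim separately. The sentence does not say that timing differs from Standard or that PRF caused the timing. A paired test within Vivostat can legitimately show that recovery occurred there between 4 and 8 months. All of this stands. A reader might infer that the interval statement has no support at all, or that the SAP itself argues from significance in one arm and not the other. The text supports neither inference.

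It can also be said that the effect of PRF is assessed in 6.1, by direct comparison at each visit. That protects the primary inference, but those tests are cross-sectional. Separation at 8 months and not at 4 is again a comparison of verdicts, not a test of change.

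The illustration can be challenged too. Opposite verdicts are common only for q of roughly 0.20-0.30. The pattern that matches the sentence, Vivostat only, never exceeds about 16%. The Cochran gate is left out. These points are fair, and the full range is shown for that reason.

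A reader might further infer a multiplicity error, since three analyses with three pairs each make up to nine McNemar tests against a correction for three. Correcting within each analysis is a common choice of family, and the plan is explicit about it. Whether to keep the pooled-sample Q is likewise a matter of preference, since no PRF claim is tied to it.

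The reply leaves one gap open: the ranking of the two intervals is untested even as pure within-group description.

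**Conclusion.** The concern holds in a limited form. The tests in 6.2 can support that recovery occurred within Vivostat. They cannot support a PRF-specific time course, because change is never compared between groups. They also cannot support ranking 4-8 months above 8-12 months, or a plateau, because the two gains are never compared.

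Under identical recovery in both groups (q = 0.15-0.50, no relapse, no Cochran gate, level 0.0167), opposite verdicts arise in about 0.4-52% of studies and Vivostat only in about 0-16%, depending on q and the McNemar version. These figures rest on assumed recovery rates. They show that the inference can mislead, not that it did so in this study.

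It would be too strong to conclude that the 12-month result is in doubt. That comparison is made directly between groups and does not depend on 6.2. The point should be corrected, but it does not threaten the primary analysis.

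**What to change.** In SAP 6.2:

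1. Add the between-group difference in the proportion of patients whose deficit status changes, for 4-8 and for 8-12 months, each with a 95% CI and an exact test. State how relapses are counted. A logistic GEE with group, visit and group-by-visit is optional; with 24 and 29 patients it would need small-sample standard errors.
2. Report the within-group change in each interval, and the difference between the two intervals, as estimates with 95% CIs. A group-by-visit term alone does not supply the second contrast.
3. Reword the interval sentence as a descriptive statement about the Vivostat group, and drop the ranking and the plateau unless these contrasts support them.

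The cost is SAP wording and a few contrasts on data already complete. The downside is imprecision. At two-sided 0.05, with nobody worsening, power to detect a between-group difference in 4-8 month recovery is 0.46 for 30% v 10%, 0.36 for 40% v 20%, 0.73 for 40% v 10% and 0.91 for 50% v 10%. The stated 0.93 does not carry over to this contrast, and the time-course statement will probably be weaker.

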2.1 Primary endpoint

The **primary endpoint** is the **presence of sensory deficit at the donor site** at postoperative follow-ups:

- Sensory deficit is assessed in a predefined skin area lateral to the incision and coded as a binary variable:
 - **0 = no sensory deficit** (normal perception in all points);
 - **1 = sensory deficit present** (numbness or altered sensation in more than three tested points).

Measurements are performed at:

Study Protocol Title: Impact of Platelet-Rich Fibrin on Donor Site Regeneration and Functional Recovery after ACL Reconstruction with BPTB Autograft

Version 01, 21 September 2020

- 4 months after surgery,
- 8 months after surgery,
- 12 months after surgery.

The primary focus of the analysis is:

1. **Between-group comparison** (Vivostat vs. Standard) of the proportion of patients with sensory deficit (0/1) at each time point, with special emphasis on the 12-month result.
2. **Within-group change over time** (4 vs. 8 vs. 12 months) in the proportion of patients with sensory deficit.

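### SAP 6.2 credits its paired tests with showing stabilization after 8 months in the PRF group, but a non-significant 8 vs 12 month McNemar test in 24 patients cannot show absence of change

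*SAP*

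**What the plan says.** SAP 2.1 lists two items as the primary focus. The second is within-group change over time ("4 vs. 8 vs. 12 months) in the proportion of patients with sensory deficit").

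SAP 6.2 gives the method. Cochran's Q is applied across the three visits, within each group and in the total sample. Then: "If Cochran's Q test is significant, pairwise McNemar's χ^2 tests will be used to compare" 4 vs 8, 4 vs 12 and 8 vs 12 months. "Bonferroni correction will be applied for these three pairwise tests", giving 0.05/3, or about 0.0167. SAP section 3 adds "All statistical tests will be two-sided" and "The nominal significance level is p < 0.05". The version of McNemar's chi-squared test (with or without continuity correction) is not stated.

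The closing sentence of 6.2 says that these analyses identify the interval of greatest recovery, and gives the answer for this study: "mainly between 4 and 8 months in the Vivostat group, with stabilization thereafter".

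The group sizes are on the SAP's opening page: "53 male patients (Vivostat n = 24; Standard n = 29". SAP section 8 says that all 53 completed follow-up. The SAP gives no definition of stabilization, no margin, and no confidence interval or power for the 8-to-12-month change.

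**The concern.** A difference test can show that change occurred. Its failure to reach significance does not show that change was absent, and in a group of 24 it says little either way. The statement in 6.2 is nevertheless attributed to the tests, on an item that SAP 2.1 places under its primary focus.

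The Bonferroni step protects against false claims of change. For a claim of no change it works the other way: the stricter the threshold, the easier it is to find nothing.

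What is at stake is the reported time course. Recovery that continues to 12 months could be described as complete by 8 months.

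**Working it through.** **Inputs from the documents.** 24 PRF patients, all followed, so 24 pairs; two-sided tests; threshold 0.05/3 = 0.0167; 79% (19/24) of the PRF group without deficit at 12 months (SAP section 7).

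**Assumptions.** No patient relapses between 8 and 12 months (varied below). The true further recovery *d* is not given in the documents, so a range is shown.

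**The plan's own power figure.** SAP section 7 states 0.93 for the 12-month between-group comparison, from a pooled z-test with 0.79 vs 0.34 and n = 24 and 29. Pooled proportion = (24 × 0.79 + 29 × 0.34)/53 = 0.544; standard error under no difference 0.1374, under the alternative 0.1210. Power = Φ((0.45 − 1.96 × 0.1374)/0.1210) = Φ(1.49) = 0.93. It reproduces, but it concerns a different comparison and says nothing about 8 vs 12 months.

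**Fewest recoveries that can be significant.** With *k* patients recovering and none relapsing, the uncorrected statistic is *k*, the continuity-corrected statistic is (*k* − 1)²/*k* (both on 1 degree of freedom), and the exact p-value is 2 × 0.5^*k*.

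| k of 24 | Share of group | Uncorrected p | Exact p | Corrected p |
|---|---|---|---|---|
| 5 | 21% | 0.0253 | 0.0625 | 0.0736 |
| 6 | 25% | **0.0143** | 0.0312 | 0.0412 |
| 7 | 29% | 0.0082 | **0.0156** | 0.0233 |
| 8 | 33% | 0.0047 | 0.0078 | **0.0133** |

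The minimum is therefore 6, 7 or 8 patients. In the uncorrected version, 6 recoveries in one interval and 5 in the other would be called change and no change, on a difference of one patient.

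**Chance of missing a real further recovery.** The number recovering is Binomial(24, *d*); the miss rate is P(*k* ≤ 5), P(*k* ≤ 6) or P(*k* ≤ 7).

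| Assumed d | Uncorrected | Exact | Corrected |
|---|---|---|---|
| 15% | 0.86 | 0.94 | 0.98 |
| 20% | 0.66 | 0.81 | 0.91 |
| 25% | 0.42 | 0.61 | 0.77 |
| 30% | 0.23 | 0.39 | 0.57 |

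At 0.05 instead of 0.0167, the 20% row would be 0.26, 0.66 and 0.66, which shows what Bonferroni adds. Relapses do not help: with a net gain of 20 points and 2.5-15% relapsing, the miss rate is 71-87% uncorrected and 90-91% corrected. Requiring Cochran's Q to be significant first can only raise these rates.

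**What the best possible data would exclude.** If 0 of 24 recovered, the exact (Clopper-Pearson) 95% upper limit is 1 − 0.025^(1/24) = 0.142, or 14 points. For 2 of 24 (illustrative) it is 27 points.

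**Do the stated figures rule out a later gain?** No. Suppose 14/24 were free of deficit at 8 months. Against 8/29 in the Standard group (illustrative), the chi-squared p-value is 0.024 uncorrected and 0.048 corrected, in line with the p < 0.05 in SAP 6.1. Moving from 14/24 to 19/24 is 5 patients, or 21 points, and with no relapses is non-significant in every version.

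**The two-interval pattern.** Suppose recovery is equal in both intervals: 25% of patients in each, 21% with deficit throughout and the remaining 29% without deficit from 4 months. Summing over all multinomial outcomes for n = 24, with Cochran's Q at 0.05 first, the pattern of 4-8 significant and 8-12 not has probability 0.29 (uncorrected), 0.29 (exact) or 0.21 (corrected).

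**The case against.** The strongest reply is that the SAP contains no rule equating p above 0.0167 with stability. The phrase is a bracketed remark on observed data, and the stated aim is comparative: to find the interval of greatest recovery. SAP 6.1 also plans counts and percentages at each visit, and section 9 allows a line plot. If the 8- and 12-month percentages are close, calling the curve flat is a fair description of the sample.

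Much of this stands. A reader might infer a formal decision rule, or that the plateau is false; the documents support neither. The 8-month PRF count is not given, and descriptive support is possible. The effect sizes in the miss-rate table are assumptions, and the SAP sets no power target for this comparison. In the equal-recovery scenario, counting both one-sided patterns would give 42-59%, but half of those would lead to the opposite statement, so 21-29% is the relevant figure.

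What does not stand is the attribution. Section 6.2 credits the tests, not the percentages or the plot, and percentages without an interval carry no precision. The threshold of 6 to 8 patients and the 14-point limit for 0 of 24 do not depend on any assumed effect.

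**Conclusion.** The point holds as one of inference: the planned tests cannot support "with stabilization thereafter" as a finding of no change. A non-significant result is guaranteed below 6, 7 or 8 recoveries when nobody relapses. It is the more likely outcome for a true further gain of 20 points in every version of the test, and for 25 points in two of the three versions. At 30 points the miss rate is still 23-57%.

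A reader might also infer that the main result is in doubt. It is not. The protocol's primary outcome is at 12 months, SAP 2.1 gives most weight to the 12-month between-group comparison, and neither depends on whether recovery in one group levelled off at 8 months. The effect is confined to the within-group time course, which makes this a change that should be made and not one that threatens the trial's principal conclusion.

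**What to change.** In SAP 6.2:

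1. Remove "with stabilization thereafter" as a conclusion from these tests.
2. For each group, report the discordant counts (recovered, relapsed) and the paired change in deficit proportion for 4-8 and 8-12 months, with a 95% confidence interval such as the Tango or Newcombe paired score interval.
3. State that a non-significant 8 vs 12 month test will be reported as no change detected, with the largest further recovery that the interval does not exclude.
4. Name the McNemar version. Say whether the correction is applied to the threshold or to the p-values, since 6.2 mentions both and applying both would correct twice.

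If the sponsor wishes to keep the word, it should be tied to the upper confidence limit lying below a stated margin. Because results are already known, such a margin must be labelled post hoc.

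The cost is SAP wording and one interval per group and visit pair from data already collected, with no new patients or procedures. The downside is a weaker statement about the plateau.

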## 9. Statistical Analysis

Descriptive statistics were used to summarize baseline characteristics. Chi-square test and t-tests were used to compare categorical and continuous variables between groups. A post-hoc power calculation for the primary endpoint was performed based on the 12-month results. All analyses were conducted using standard statistical software.

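### The SAP concludes that the sample size was sufficient from power computed at the observed 12-month result, and plans no confidence interval for the primary endpoint

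*SAP*

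**What the plan says.** SAP section 7 enters the observed 12-month proportions without deficit (0.79 Vivostat, 0.34 Standard) and the achieved group sizes (24 and 29) into a two-sided pooled z-test at 0.05. It reports an achieved power of 0.93, "indicating that, despite being a pilot study, the sample size was sufficient to detect the observed effect size at 12 months with high probability". The section closes with a qualification: "This power calculation is descriptive and does not change the interpretation of the primary analysis".

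Protocol section 9 matches this: "A post-hoc power calculation for the primary endpoint was performed based on the 12-month results". Neither document states a target difference, a planned sample size or a calculation made before the results were known.

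For the between-group analysis of the primary endpoint, SAP section 6.1 says: "Results will be reported as in Table 3, with counts, percentages, and p-values". SAP section 3 summarizes categorical variables by frequencies and percentages only. Neither document mentions a confidence interval or a between-group effect estimate.

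**The concern.** A sample size is adequate, or not, for an effect chosen independently of the result. When the observed proportions are treated as the true ones, the power is fixed almost entirely by the p-value: a significant result yields power above one half and a non-significant result yields power below it. The sentence in section 7 therefore presents the significance of the result a second time, as if it were evidence about the design.

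This is the only statement in either document that speaks to the adequacy of 53 patients. It is also worded to offset the pilot status of the study, where precision matters most. Because no interval is planned, a reader sees 0.93 and a small p-value but nothing on how uncertain the 12-month difference is.

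**Working it through.** **Inputs.** SAP section 7: p1 = 0.79, p2 = 0.34, n1 = 24, n2 = 29, two-sided alpha 0.05, pooled z-test. Assumed, because not printed: counts without deficit of 19/24 (79.2%) and 10/29 (34.5%). No other integers out of 24 and 29 round to 79% and 34%.

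**1. Reproducing 0.93.** With the pooled standard error under the null (SE0) and the unpooled one under the alternative (SE1):

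power = Φ[(|p1 − p2| − 1.96 × SE0) / SE1], ignoring the negligible opposite tail.

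- Pooled proportion = (24 × 0.79 + 29 × 0.34) / 53 = 0.5438
- SE0 = √[0.5438 × 0.4562 × (1/24 + 1/29)] = 0.1374
- SE1 = √[0.79 × 0.21/24 + 0.34 × 0.66/29] = 0.1210
- (0.45 − 1.96 × 0.1374) / 0.1210 = 1.49, and Φ(1.49) = 0.932

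With 19/24 and 10/29 the same formula gives 0.929. Both agree with the SAP.

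**2. Why this says nothing about adequacy.** The test is significant exactly when |p1 − p2| > 1.96 × SE0. That is also exactly when the numerator above is positive, so that Φ exceeds 0.50. To confirm this in the actual design, all 25 × 30 = 750 tables were enumerated. Four degenerate corners were excluded, leaving 746, and in each table the observed proportions were taken as true:

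| Result (uncorrected chi-square) | Tables | Power at observed effect |
|---|---|---|
| p < 0.05 | 454 | at least 0.500 (minimum 0.5002) |
| p ≥ 0.05 | 292 | at most 0.498 (maximum 0.4977) |

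With the Standard group held at 10/29, the power follows the p-value:

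| Vivostat | p | Power at observed effect |
|---|---|---|
| 15/24 | 0.042 | 0.53 |
| 17/24 | 0.0084 | 0.77 |
| 19/24 | 0.0011 | 0.93 |

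**3. What the same design can detect.** With the Standard rate at 10/29, power is 0.31 for a true increase of 20 points, 0.59 for 30 points and 0.85 for 40 points. The increase detectable with 80% power is about 38 points at a control rate of 34%, and 33 to 38 points for control rates from 10% to 55%.

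**4. The missing interval.** For 19/24 versus 10/29:

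- Difference d = 0.7917 − 0.3448 = 0.447
- Wilson 95% limits: 0.595 to 0.908 (Vivostat) and 0.199 to 0.527 (Standard)
- Newcombe lower limit = 0.447 − √[(0.792 − 0.595)² + (0.527 − 0.345)²] = 0.179
- Newcombe upper limit = 0.447 + √[(0.908 − 0.792)² + (0.345 − 0.199)²] = 0.633
- p = 0.0011 (chi-square), 0.0029 (continuity-corrected), 0.0020 (Fisher), all consistent with the p < 0.01 in SAP section 6.1

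If the true difference were at the lower limit of 18 points, the power of this design would be 0.26.

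**The case against.** The SAP hedges the statement. It labels the calculation post hoc, limits it to the observed effect, acknowledges the pilot status and calls the figure descriptive. No test, population or decision depends on 0.93, and neither document says that 53 patients were chosen because of it. All of that is true and limits the damage. But confining the claim to the observed effect is what makes it circular, and calling the figure descriptive leaves the conclusion about sufficiency standing.

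Power at the observed effect is also not a strict function of p. Across tables with p from 0.0005 to 0.002 it runs from about 0.88 to 0.96. That is why it is described here as essentially, not exactly, a restatement. The division at 0.50 does not depend on this.

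On the interval, a reader could compute one from the counts that section 6.1 promises, and it would exclude zero. This is fair: the omission does not change the direction or significance of the result. It still leaves the main estimate of the study and its precision for readers to work out.

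Finally, a detectable difference computed at the observed 34% control rate is itself partly built on the results. That is correct, so it should be optional and labelled.

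**Conclusion.** The concern holds. The figure of 0.93 is correct, but the conclusion that the sample size was sufficient does not follow from it, and the primary endpoint has no planned effect estimate or confidence interval. Under the inferred counts the 12-month difference is 44.7 points, with a 95% CI from about 18 to 63 points.

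The interval rests on those counts and is unadjusted. SAP section 4 itself refers to a non-randomized cohort, so the interval reflects sampling error only and not confounding. The enumeration needs only the two group sizes and the stated test. The significance and direction of the 12-month result are not in dispute. This should be fixed, but it does not invalidate the analysis.

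**What to change.** - **SAP section 7.** Delete the clause that draws the sufficiency conclusion. Either drop 0.93, or keep it with a statement that it was computed at the observed effect and does not bear on whether the sample size was adequate. State that no prospective sample-size calculation is documented.
- **Optional in section 7.** If a sensitivity statement is wanted, give the detectable increase for 24 versus 29 at two-sided 0.05 and 80% power: about 38 points, labelled as assuming the observed control rate of 34%.
- **SAP section 6.1 and Table 3.** Add the 12-month risk difference (Vivostat minus Standard, proportion without deficit) with a 95% CI beside the p-value, labelled as unadjusted in a non-randomized cohort. The Newcombe method suits these group sizes; whichever method is used should be named.
- **Protocol section 9.** Bring the power sentence into line with the revised section 7. It makes no sufficiency claim itself, so this matters mainly if the calculation is dropped.

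The cost is a few sentences and one added estimate from data already in hand. No test, population or data collection changes. The sponsor gives up a favourable-looking figure.
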